4.3.5 Intervention clusters: PEBRA model

The participants in the intervention clusters are offered the PEBRA model. In the PEBRA model the ART visit/refill is coordinated by the PE, as much as feasible according to the participants' preferences. Thus, the preferences of each participant are captured at enrolment and after a strict schedule thereafter. The PE conducts the preference assessment using a tablet-based application, called PEBRAApp. The PEBRAApp will automatically alert the PE when the next preference assessment of each participant is due. The preference assessment interval is independent from the ART refill interval and can be performed via phone as well. Participants with a suppressed VL will get a preference assessment every 3 months and participants with unsuppressed VL a preference assessment every month. As a strict part of the preference assessment, the PE asks two psychosocial questions ("Is there anything you would like to share with me today?" / "How do you think you are doing today?") and for those patients with unsuppressed VL an additional third question ("Do you have a safe environment to take your medication?").

The preference assessment works as a two-step approach: First, the participant will be asked his/her preference regarding different domains of DSD (see below) and this will be entered into the PEBRAApp. Secondly, the chosen preferences are assessed regarding feasibility with specific questions, as not all preference options are available to everyone all the time, e.g. no nearby Village Health Worker (VHW) available who could dispense ART, or no Community Youth Club (CYC) established in the participants' community, or home-delivery by PE not feasible.

The preference assessment entails the following three domains of DSD:

- 1) ART Refill
- 2) SMS notifications
- 3) Support

For each domain, the following options can be chosen:

- 1) ART Refill (one option possible):
 - a. At the clinic
 - b. Village Health Worker (VHW) in the community
 - c. Home-delivery by the PE
 - d. Through a Community Adherence Club (CAC)
 - e. Through a Treatment Buddy
- 2) SMS notifications (several options possible):
 - a. Adherence reminder: Frequency (to be chosen) and pre-defined message (to be chosen)
 - b. Refill visit reminder: Frequency (to be chosen) and pre-defined message (to be chosen)
 - c. VL-triggered message after blood draw as soon as VL result is available: pre-defined message for "unsuppressed" and "suppressed" (to be chosen)

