- 3) Support (several options possible):
 - a) By the nurse at the clinic
 - b) Saturday Clinic Club (SCC)
 - c) Community Youth Club (CYC)
 - d) Phone Call by PE
 - e) Home-visit by PE
 - f) School visit and health talk by PE
 - g) Pitso visit and health talk by PE
 - h) Condom demonstration
 - i) More information about contraceptives
 - j) More information about VMMC
 - k) For pregnant: Linkage to young mothers group (DREAMS or Mothers-to-Mothers)
 - l) For females: Linkage to a female WORTH group (Social Asset Building Model)
 - m) Legal aid information
 - n) Show me tuneme.org (teenage topics)
 - o) Show me Ntlafatso Foundation Facebook (HIV stigma/discrimination topics)
 - p) No support wished

Every PE who delivers PEBRA model receives a tablet, that has a calling function and the PEBRAApp installed. PEBRAApp is protected by a password, only known to the PI and the PE, and does not entail confidential patient information, i.e. names. PEBRAApp serves as a data collection tool (baselines assessment, preference assessment, etc.) and as a patient management tool to keep track of the ART refill of each participants (WHERE and WHEN) and his/her chosen support. PEBRAApp will keep overview of all due dates (next ART refill date, next preference assessment date) and automatically alert the PE for an action.

The PEBRAApp helps the PE to assess each participants' preference, to adapt the ART refill according to these preferences in a feasible manner, to keep track of the ART refill, and to ensure regular contact between the PE and the participant. The chosen SMS notifications will be sent automatically through an external platform (VL platform, www.lstowards909090.org/db), and always include a call-back option to the PE's number.

The PEBRA model as well as the PEBRAApp have been developed and refined in several multi-stakeholder workshops together with adolescents and young people (Sentebale PEs, Sentebale Youth staff, AYPLHIV, various youth club members from urban and rural areas, international and national App developers). Figures 1a and 1b illustrate the PEBRA model and Figures 2a and 2b the PEBRAApp. Under the following link (<https://bit.ly/2TA5RA5>) a prototype version of PEBRAApp can be accessed.

FIGURE 1a. Schematic description of PEBRA model for AYPLHIV

[figure not shown]
[figure not shown]
[figure not shown]
[figure not shown]

FIGURE
1a. Schematic description of PEBRA model for AYPLHIV

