5.1 Primary endpoint

In care with documented viral suppression at 12 months, defined as the proportion of participants in care with a documented VL <20 copies/mL 12 months (range: 9 – 15 months) after enrolment out of all participants enrolled

- i. *Rational for VL suppression level at 20 copies/mL: VL determination will be done on COBAS TaqMan® HIV-1 Test, v2.0 (Roche Diagnostics) using plasma, and has a reliable lower limit of detection of 20 copies/mL*
- ii. *Definition of "in care": at least one ART visit in the defined window*
 - I. *Including participants who transferred out to any other health facility with known outcome (documented proof of follow-up visit or laboratory test)*
 - II. *Excluding participants who died (all-cause), were lost to follow-up (LT FU), or were known defaulters/refusers, i.e. were more than 2 months late for ART refill with a reason available (e.g. currently no money for clinic-visit, busy working in South Africa, etc.)*
- iii. *The study will use VL results from routine VL monitoring. To synchronize routine VL monitoring and study VL monitoring, study staff will help ensure each site has the capacity to collect these samples and will support existing systems that help to provide results back to sites. VLs will only be performed on individuals who return for visits and no tracking will be performed by the study staff to obtain VLs.*

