5.2 Secondary endpoints

- a) Adherence to ART at 3 months (range 2.5 – 3.5), 6 months (range 5 – 8) and 12 months (range 9 – 15) after enrolment
 - i. *Assessed by 4 different setting- and age-validated ART adherence questions²⁰⁻²²:*
 - a. *pill count: change in percentage*
 - b. *"When was the last time you missed any medications?" [i) past week, ii) 1-2 weeks ago, iii) 3-4 weeks ago, iv) never]: Dichotomous outcome missed doses vs. no missed doses in the past month*
 - c. *"ART missed at two or more consecutive days within last month?" ("drug holiday" question)*
 - d. *"How would you rate your adherence over the last month" [i) very poor, ii) poor, iii) fair, iv) good, v) very good, vi) excellent]: Dichotomous outcome adherent vs non-adherent (anything less than 'excellent')*
- b) Quality of Life (QoL) at 6 months (range 5 – 8) and 12 months (range 9 – 15) after enrolment
 - i. *Assessed by WHO QoL in PLHIV: WHO HIV QoL questionnaire (whoqol_hiv_bref questionnaire with 31 five-point Likert Scale items with categorical outcome)²³⁻²⁵*
- c) Perceived quality of ART Care (QoC) / patient service satisfaction at 6 months (range 5 – 8) and 12 months (range 9 – 15) after enrolment
 - i. *Assessed by a setting-validated QoC and patient service satisfaction questionnaire (12 five-point Likert Scale items with categorical outcome)²⁶ by an external data collector, not the PE*

- d) Engagement in care at 6 months, defined as the proportion of participants engaged in care 6 months (range 5 – 8) after enrolment out of all participants enrolled
 - i. *Definition of “in care”: at least one ART visit in the defined window*
 - I. *Including participants who transferred out to any other health facility with known outcome (documented proof of follow-up visit or laboratory test)*
 - II. *Excluding participants who died (all-cause), were lost to follow-up (LTFU), or were known defaulters/refusers, i.e. were more than 2 months late for ART refill with a reason available (e.g. currently no money for clinic-visit, busy working in South Africa, etc.)*
- e) Alternative viral suppression at 12 months, defined as the proportion of participants with a documented VL <1000 copies/mL 12 months (range 9 – 15) after enrolment out of all participants enrolled
 - i. *Rational for alternative VL suppression definition at 1000 copies/mL: According to the currently used Lesotho national guidelines, an unsuppressed VL is defined as a 1000 copies/mL or more*

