- f) Engagement in care at 12 months, defined as the proportion of participants engaged in care 12 months (range 9 – 15) after enrolment out of all participants enrolled (definitions see above under d)
- g) All-cause mortality at 6 and 12 months, defined as the proportion of participants dead 6 months (range 5 – 8) and 12 months (range 9 – 15) after enrolment, respectively, out of all participants enrolled
 - i. *Verbal autopsy to capture cause of death whenever possible. No death certificate or autopsy report required.*
- h) LTFU at 6 and 12 months, defined as the proportion of participants LTFU 6 months (range 5 – 8) and 12 months (range 9 – 15) after enrolment, respectively, out of all participants enrolled
 - i. *We define participants lost to follow-up if they or their treatment buddies were more than 2 months late for a scheduled consultation or medication pick-up and no information was found about the participant*
- i) Transfer out at 6 and 12 months, defined as the proportion of participants who transferred out to any other health facility (than the initially attached one) with known outcome (documented proof of follow-up visit or laboratory test) 6 months (range 5 – 8) and 12 months (range 9 – 15) after enrolment, respectively, out of all participants enrolled

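### Loss to follow-up (LTFU) turns on whether information was found, and peer-educator contact makes that likelier in the intervention arm, so the comparison risks unequal ascertainment, probably favouring PEBRA

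*Combined protocol and SAP*

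**What the plan says.** Section 5.2(h) makes LTFU at 6 and 12 months a between-arm secondary endpoint. It needs two conditions: the participant or treatment buddy is "more than 2 months late for a scheduled consultation or medication pick-up and no information was found about the participant".

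Sections 5.1 and 5.2(d) define a neighbouring group, known defaulters and refusers, who "were more than 2 months late for ART refill with a reason available". Both groups are excluded from being in care. A participant who transferred out with documented proof of follow-up elsewhere counts as in care.

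Section 4.3.5 sets the intervention contact schedule: "Participants with a suppressed VL will get a preference assessment every 3 months and participants with unsuppressed VL a preference assessment every month". The assessments may be done by phone. Peer-educator (PE) calls and home visits are among the support options, and the app is meant "to ensure regular contact between the PE and the participant". Section 4.3.6 describes control care as nurse-coordinated and mostly clinic-based, with no PE contact schedule.

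On timing, the LTFU, death and transfer endpoints are each read at "12 months (range 9 – 15) after enrolment, respectively, out of all participants enrolled", with a parallel 5–8 month range for the 6-month reading. No day within a range is named.

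**The concern.** Two participants who stopped attending on the same date get different labels if someone learned why in one case and not in the other. The endpoint therefore mixes two things: how many people stopped coming, and how often staff found out the reason. The intervention acts directly on the second. The trial is open-label (Section 4.3.8), and the plan sets neither equal tracing steps nor an assessor independent of arm for LTFU. Its only statement on tracing, in Section 5.1, concerns obtaining viral loads.

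At stake is a named secondary result. LTFU could look lower under PEBRA when attendance is the same. Known default, where many reclassified people would go, is not a row in Table 1, so the offsetting rise might not be seen. Section 11.2.2 mentions a Poisson model for attrition but does not say whether LTFU is included.

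A separate gap is the reading date. Nothing says on which day of the range status is taken, or how to class someone who is more than 2 months late and then returns within it.

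**Working it through.** **1. The plan's own figure.** The plan gives no expected LTFU rate and no power for LTFU. Section 11.1 gives 90% power for viral suppression: 300 participants, 20 clusters, ICC 0.05, 70% in control and a 20% increase (read as 70% to 90%).

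- Design effect = 1 + (15 − 1) × 0.05 = 1.70.
- Effective size per arm = 150 / 1.7 = 88.2.
- SE = √[(0.7×0.3 + 0.9×0.1) / 88.2] = 0.0583, and 0.20 / 0.0583 = 3.43.
- Power from a noncentral t on 18 df (20 clusters − 2), two-sided 0.05: 90.0%.

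The stated figure reproduces, so the same method serves for LTFU. Using the design effect of 1.7 for LTFU is an assumption.

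**2. Model for LTFU.** Let q be the share more than 2 months late, equal in both arms, and f the chance that information is found. Then LTFU = q × (1 − f). The documents give neither q nor f, so both are assumed and varied.

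**3. One case in full.** Take q = 15%, with f = 30% in control and 70% in intervention.

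- Control: 0.15 × 0.70 = 10.5%. Intervention: 0.15 × 0.30 = 4.5%.
- OR = (0.045/0.955) / (0.105/0.895) = 0.40.
- SE = √[(0.105×0.895 + 0.045×0.955) / 88.2] = 0.0394, and 0.06 / 0.0394 = 1.52.
- Two-sided rejection rate: 30.3%, with no true difference in lateness.

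**4. Range.** Two-sided rejection rates by the same formula, with f given as control→intervention:

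| Late in both arms | 30→40% | 50→60% | 30→50% | 50→70% | 30→70% |
|---|---|---|---|---|---|
| 10% | 5.8% | 6.1% | 8.3% | 9.9% | 21.3% |
| 15% | 6.2% | 6.6% | 10.1% | 12.5% | 30.3% |
| 20% | 6.6% | 7.2% | 12.1% | 15.4% | 39.4% |
| 30% | 7.6% | 8.6% | 16.7% | 21.5% | 57.3% |

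With equal f the rate is 5% and the OR is 1. These are normal-theory approximations to the planned mixed logistic model, and they are rough where counts are small.

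**5. Reading day.** Under an assumed constant LTFU hazard of 2% a month, cumulative LTFU is 1 − 0.98^k: 16.6% at 9 months, 21.5% at 12 and 26.1% at 15. The reading day matters to the level. Because the range is the same in both arms, it produces an arm difference only if reading times differ by arm.

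**The case against.** The strongest reply is that the contrast in contact is smaller than it looks. Control clusters also have a trained PE who does screening and baseline (Section 4.3.4). Adherence is assessed at 3, 6 and 12 months, and quality of life and of care at 6 and 12 months, in both arms (Section 5.2). PE calls and home visits are choices, and a participant may decline all support. Follow-up data come primarily from routine facility records (Section 12.1). Closer PE follow-up might also detect lateness more completely, which would push the other way. All of this stands. It limits the likely size, but it does not remove the scheduled extra contact in one arm or supply an equal-checking rule.

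A second reply is that engagement in care already pools everyone not attending, so a reader would see equal engagement beside lower LTFU. That is partial protection. It does not correct the LTFU contrast itself.

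Two stronger readings are tempting. A reader might infer that the LTFU comparison is biased as a matter of fact. The documents give no lateness or information-found rates, so only a risk with a probable direction is supported. A reader might also infer that the 9–15 month range favours PEBRA. It is common to both arms, and nothing says that reading times differ by arm.

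**Conclusion.** The concern holds as a risk of differential ascertainment in the LTFU endpoint, probably in PEBRA's favour and of unknown size. It rests on information being found more often in the intervention arm. That is likely from the contact schedule but not quantified in the plan. A modest gap would raise the false-positive rate only a little; the 30% figure needs an assumed 40-point gap at 15% lateness and should not be quoted alone.

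The missing reading day is a separate definition gap that costs precision.

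Moving people between LTFU and known default changes neither the primary endpoint nor engagement in care, since both groups are excluded from being in care. There is one narrower route to those endpoints: a transfer counts as in care only if documented, so unequal searching for transfers could reach them. This is worth correcting before analysis, at the level of a secondary endpoint.

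**What to change.** For the between-arm comparison, define the endpoint as more than 2 months late on a fixed day, with no documented death or transfer, whether or not a reason is known. With the plan's 30-day month, the natural days are 180 and 360. Report the LTFU/known-defaulter split descriptively by arm.

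Read death and transfer status on the same fixed days, using the same record-checking steps in both arms and preferably someone other than the PE. The new definition still depends on finding deaths and transfers, so this part is needed as well.

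**Cost.** The definition is a wording change using existing refill records; equal record checks add some staff time. The endpoint will no longer match the plan's LTFU definition, and it overlaps with engagement in care. Day 360 must also fall within follow-up for the last enrolee. Five months of recruitment plus 12 months is 17 months, which fits the 18 months in Section 16. It does not fit the October 2020 end in Figure 3: an August 2019 start plus 17 months is January 2021. The data cut-off should be stated accordingly.

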5.3 Safety Endpoint

We specifically assess the safety of our PEBRA model, defined as the proportion of participants experiencing a Serious Adverse Events (SAE) within 12 months after enrolment out of all participants enrolled. See chapter [12.4](#) for a detailed description of SAEs.

TABLE 1. Summary of PEBRA study endpoints

endpoints	Following enrolment		
	At 3 months (range: 2-5 – 3.5)	At 6 months (range: 5-8)	At 12 months (range: 9-15)
In care with documented viral suppression <20 copies/ml			Primary
Adherence to ART	Secondary	Secondary	Secondary
QoL	Secondary	Secondary	Secondary
QoC	Secondary	Secondary	Secondary
In care with documented viral suppression <1000 copies/ml			Secondary
Engagement in care		Secondary	Secondary
All-cause mortality		Secondary	Secondary
LTFU		Secondary	Secondary
Transfer out		Secondary	Secondary
SAE			Safety

Note: we consider 1 month = 30 days

6 BIOMOLECULAR RESEARCH

In the frozen 12-month follow-up blood samples, we may assess ART drug levels as a marker for adherence. This analysis would be done in collaboration with Department of Biomedicine at University of Basel that are part of this research consortium. These samples would fall under attached Material Transfer Agreement, submitted together with this study protocol (see Appendix 18.4) for approval.

7 QUALITATIVE RESEARCH

Besides above outlined qualitative research (QoL, QoC, longitudinal description of participants' preference assessments) we will explore the acceptability of the PEBRA model in a) Focus Group Discussions (FGD) with study participants from the intervention clusters, and b) key informant interviews (KII) with the main stakeholders (District Health Management Team and different health center staff). We plan to conduct at least 2 FGD (with about 5 study participants) per district and 3 KII per district, according to the concept of saturation. Data will be collected by trained facilitators using piloted interview questionnaires and discussion guides, in the local language (Sesotho). Qualitative data will be recorded, transcribed, translated into English and coded and analyzed using the Framework Method.²⁷ All participants in this qualitative research will be required to sign a separate consent form to participate and to be recorded. These consent forms and interview questionnaires will be submitted as an amendment to the ethics committee in Lesotho at a later stage.

8 COST-EFFECTIVENESS ANALYSIS AND SYSTEM IMPACT EVALUATION

We will perform a system impact evaluation and cost-effectiveness analysis, in order to estimate the impact of the PEBRA model on health benefits and costs. First, we will assess the direct costs of the PEBRA model. Secondly, we will assess the cost-effectiveness of the PEBRA model. Thirdly, we will assess the economic burden of the PEBRA model to the study participants, i.e. including both direct costs and the opportunity costs of their time. The assessment of direct costs includes staff costs (PEs, clinic staff, VHWs), personnel training costs (especially for the PEs), the cost of equipment needed (PEBRAApp, logistics), medical costs to the participant (medication, laboratory tests, consumables, etc.), and non-medical costs to the participant (i.e. cost of transportation to ART service). Data to assess patient level costs will be collected from a randomly selected sub-sample of study participants from each cluster arm, using medical expenditure records and interviews. Cost outcomes will include:

- i) The average cost to the service provider per patient achieving the primary endpoint at 12 months in each cluster arm ('per patient suppressed provider cost')
- ii) The average cost to the patient per patient achieving the primary endpoint at 12 months in each cluster arm ('per patient suppressed patient cost')
- iii) The annual cost per patient in each cluster arm ('per patient year cost')
- iv) The cost-effectiveness of the PEBRA model with respect to viral suppression and engagement in care

Costs will be reported as means (incl. standard deviations) and medians (incl. interquartile range) in local currency and US dollar and International Dollar.

9 PREFERENCE AND FEASIBILITY ASSESSMENT

We will systematically assess the following exploratory analyses regarding feasibility and youth ART service preference:

- 1) Youth ART service preferences: Longitudinal description of participants' preference assessments
- 2) Feasibility of youth ART service according to preferences: Percentage of ART service delivered according to participants' preferences
- 3) Differentiated Impact of the different support options on key study outcomes

10 PILOT TRIAL

PEBRA model will be piloted at one representative health facility in Butha-Buthe district, that will be pragmatically chosen in collaboration with the District Health Management Team. The pilot trial will be crucial to assess feasibility of the PEBRA model and the study procedures. The same procedures apply in the pilot trial as outlined in section 4.3.4 and 4.3.5, using the same consent process and baseline data collection. One PE will be specifically trained for the pilot. Recruitment for the pilot will be closed once 3-5 study participants are enrolled and follow-up will last for 2.5 months after having enrolled the last participant. All endpoints that are mentioned in Table 1 under "At 3 months (range 2.5 – 3.5)" will be assessed and analyzed. The aim of the pilot trial is to give a first insight into PEBRA model and provide detailed information for the main trial.

11 SAMPLE SIZE AND ANALYSIS PLAN

11.1 Sample size calculation

Based on data from our database with VL results from all health facilities of Butha-Buthe and Mokhotlong district (VL platform, www.1stowards909090.org/db), there are on average 15 AYPLHIV per health center with an overall viral suppression rate of 70%, thus, we expect this proportion of viral suppression for the control clusters. An overall target sample size of 300 AYPLHIV in 20 clusters (10 per arm) will provide us 90% power (design effect of 1.7) to detect a 20% increase of viral suppression in the intervention group, assuming a type 1 error of 0.05, and an intra-cluster correlation coefficient (ICC) of 0.05, an ICC based on similar studies^{28,29}.

